Research Title: Vitamin D Supplementation Effect In Children With Pulmonary Tuberculosis Treatment: Randomized Double Blind Controlled Trial

Principal Investigator: dr. [name], Sp.A

Expertise: Pediatrics
Position: Doctoral Student

E-mail: [contact]

Institution: Program Pascasarjana Program Studi Doktor Fakultas Kedokteran Universitas Padjadjaran

Institution e-mail: [contact] Sponsor: Individual (Principal Investigator)

Clinical Monitor: Dr. dr. [name], M.H., M.M., FISQua

Investigator teams:

[name]. [name], dr., Sp.A(K), M.Kes Prof.Dr.[name], dr., Sp.A(K), M.Sc Ph.D Dr.[name], dr., Sp.A(K)

Disclaimers: The investigators have no potential conflict of interest

Source(s) of support/funding: No funding or other financial support was received.

Disclosure of relationships and activities: none declared

Ethical issues: The contributing investigators have no potential ethical issues.

Document Last Update Date: 1 June 2021

Summary of Clinical Trial Protocol

Study Description:

This randomized, double-blind control trial with a cohort design was conducted in Bethesda Hospital West Borneo from December 2020 - May 2021. The inclusion criteria were children between 6 to 18 years old, newly diagnosed with pulmonary tuberculosis with vitamin D insufficiency. Diagnosis of the tuberculosis case was based on The Indonesian Pediatric Tuberculosis Scoring System. It consists of history taking and laboratory findings that support tuberculosis common symptoms such as household contact, prolonged fever more than two weeks, non-remitting cough more than three weeks, and decrease body weight, and lymph node enlargement; laboratory findings include Tuberculin Skin Test (TST) and chest X-ray (CXR). Scoring ranges from 0 to 3 for each variable with a total score of more than six is considered as tuberculosis diagnosis. Patients also collect the sputum for gram staining and Xpert MTB/RIF examination. The isolation of Mycobacterium tuberculosis was not done in this study because of limited resources.

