At recruitment, study staff enrolled patients consecutively according to the order of arrival of patients from number 1 to 84. Study staff who assigned patients to active drugs or placebo did not know the following assignment in the sequence because they did not have access to the study code. Treatment allocations were hidden from patients and research staff. Those who analyzed the data were not covered for group assignments. Monitoring of subjects medication adherence and daily symptoms conducted by using a checklist table filled out by the patient's parents and confirmed check by the researcher during the patient follow-up schedule to the clinic.

All subjects received antimicrobial treatment for tuberculosis drugs in the form of a fixed-dose combination. Patients were reviewed on 14, 28, 42, and 56 days after starting antimicrobial treatment; body weight and height were measured at each time point. After the intensive phase of antimicrobial treatment, patients were monitored monthly. A repeated vitamin D level by ELISA and liver function test were done six months after starting the antimicrobial treatment.

Clinical Trial Process

- a) Administration of intervention (dose regimen, invasive and non-invasive measures, comparison drugs, placebo): Pediatric patients diagnosed with TB and vitamin D insufficiency will be given vitamin D supplementation of 1000IU/day for six months. Giving a placebo in the control group will get one dose of placebo/day for six months. Vitamin D and placebo preparations are prepared in the same colored bottles containing vitamin D or a placebo.
- b) Determination of outcome indicators:
 After six months of treatment, the patient will have his vitamin D level checked.
- c) Interim analysis plan: sputum examination is performed every two weeks during the intensive phase of antituberculosis treatment.
- d) Clinical trial termination procedure:

Parents of patients who refuse to be included in this study can stop the administration of vitamin D supplementation by reporting to the doctor in charge of the service during control at the pediatric outpatient clinic at Bethesda Hospital, West Kalimantan. Patients who do not complete treatment for six months (including unexpected events) will be discontinued from participating in the study and explained to parents that TB treatment is continued but not included in the study, and the test drug package will not be continued.

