- e) Estimated research time required for one subject per one course of action: 5 minutes per action of blood and phlegm examination.
- f) Ethical issues (state your opinion on ethical issues in research that may be encountered):
- Respect for someone (respect for human dignity):

Researchers provide information to parents of research to be carried out, including procedures, benefits, risks, volunteering, and data confidentiality. Information is provided so that the subject's parents can determine whether their child can participate in the study or not. Parents are free to make their own decisions. Subjects' parents who voluntarily participated in this study were then asked to express written consent by signing informed consent.

• Beneficence (beneficial) non-maleficence (not harmful):

There is no physical risk to the child who is the subject of the study, but it can cause it to occur. The benefits of this research are not felt directly by the child/parent. However, the willingness to be a subject will be significant to obtain information on routine vitamin D levels in children with tuberculosis. It can be used as input and the essential information to provide vitamin D supplementation in children with tuberculosis. Suppose the examination results reveal a vitamin D deficiency. In that case, the child will receive vitamin D supplementation at no charge to the parents.

• Justice (fairness):

All subjects are treated equally in the study and are given the same opportunity to be included, which is carried out in a fair and balanced manner.

Adverse Event (AE) reporting plan

- a. Recording (Things to be reported): symptoms of side effects of antituberculosis treatment such as jaundice, nausea, and vomiting.
- b. Analysis and procedure of action: the patient will be examined for liver function. If the liver function increases, antituberculosis drugs will be discontinued.
- c. Emergency rescue system: patients who feel there are complaints of nausea, vomiting, and jaundice will go to the Children's Clinic, Bethesda Hospital, West Kalimantan.
- d. Discontinuation of subjects in the study due to adverse events: the administration of antituberculosis drugs will be discontinued, and patients will not be included in the study.

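### The termination procedure and the adverse-event plan give opposite statements about tuberculosis drugs for a child withdrawn early because of an adverse event

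*Protocol*

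**What the plan says.** Two places in the protocol deal with a child who leaves the study early.

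- **Clinical Trial Process, item d (termination procedure).** The scope is wide: "Patients who do not complete treatment for six months (including unexpected events) will be discontinued from participating in the study". For these children it is "explained to parents that TB treatment is continued but not included in the study", and the study preparation stops.
- **Adverse Event (AE) reporting plan, item d.** "Discontinuation of subjects in the study due to adverse events: the administration of antituberculosis drugs will be discontinued". The same sentence also takes the child out of the study.

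Three other statements bear on how these are read. Item a of the Clinical Trial Process fixes the study preparation at six months: children "will be given vitamin D supplementation of 1000IU/day for six months", with placebo for the same period. Item a of the adverse-event plan lists what is recorded: "symptoms of side effects of antituberculosis treatment such as jaundice, nausea, and vomiting". Item b of that plan gives a conditional rule: "If the liver function increases, antituberculosis drugs will be discontinued".

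None of these items refers to another, writes an exception, or says which prevails.

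**The concern.** One item says that tuberculosis treatment goes on after the child leaves the study. The other says that the tuberculosis drugs are stopped when the reason for leaving is an adverse event. If both cover the same child, clinic staff have two opposite statements. The parents may also be told that treatment continues when the adverse-event plan has it stopped.

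What is at stake is the care of a child with tuberculosis and the accuracy of what the parents hear. The statistical analysis is not at stake. Both items end the child's participation, so sample size, completer status and outcome data are the same whichever is followed.

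**Working it through.** No formula applies to the conflict itself, so the check sets the two items side by side and asks whether one child can fall under both.

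| | Clinical Trial Process, item d | AE reporting plan, item d |
|---|---|---|
| Who is covered | Any child not completing six months of treatment, unexpected events included | Any child discontinued because of an adverse event |
| Laboratory or severity condition | None | None |
| Participation in the study | Ends | Ends |
| Tuberculosis drugs | Continued, outside the study | Discontinued |
| Exception or cross-reference | None | None |

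**Overlap.** Take a child withdrawn before six months for an adverse event.

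1. The child meets the condition of the adverse-event item directly.
2. The termination item depends on what its word for treatment means.
   - If it means the study preparation, the child does not complete it, because the adverse-event item says the drugs "will be discontinued, and patients will not be included in the study".
   - If it means the tuberculosis drugs, the child does not complete them, because the adverse-event item stops them.
3. The child is therefore covered by both items. It does not matter whether an unexpected event is the same as an adverse event, since failing to complete six months is enough.
4. The instructions on the tuberculosis drugs are opposite.

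**Does item b of the adverse-event plan settle it?** Item b stops the drugs on a raised liver result. Item d of the same plan carries no such condition.

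- If d stands alone, a child withdrawn for nausea or vomiting without a raised liver result is covered by d and by the termination item, and the conflict is complete.
- If d applies only where b does, a child with a raised liver result who is withdrawn early is still covered by the termination item. The conflict is narrower but remains.

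**Could the wording still have affected children on treatment?** The Study Description says the trial "was conducted in Bethesda Hospital West Borneo from December 2020 - May 2021", and the document is dated 1 June 2021.

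- Start on 1 December 2020, plus six months = 1 June 2021 (31 + 31 + 28 + 31 + 30 + 31 = 182 days), which is the document date.
- Start on 2 December 2020, plus six months = 2 June 2021.
- Start on 31 May 2021, plus six months = 30 November 2021.

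If the stated months are the enrolment period, which is an assumption, every course started after 1 December 2020 would end after the document date, between 2 June and 30 November 2021. If they are the whole trial period, treatment was over and only the report is affected.

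**The case against.** The best defence is that the items stand as general rule and specific rule. The termination item tells parents that leaving the study does not end tuberculosis care. The adverse-event plan then reads as one sequence: side effects are recorded, liver function is tested, the drugs are stopped if it is raised, the child attends the clinic, and the consequence for the study follows. On that reading item d of the plan only restates the outcome of item b. It can also be said that neither item calls the stop permanent, so the drugs might be resumed later outside the study.

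This is a plausible account of what was intended, but the protocol writes none of it. It states no exception and no resumption. The termination item also extends itself to unexpected events and leaves no room for a separate adverse-event rule. Even if item b limits item d, the children with raised liver function remain under both items.

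Some of the objection does stand.

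- The natural meaning of treatment in the termination item is the study preparation. The other meaning strains that item, because it would then say that a treatment not completed is continued. The overlap holds on the natural meaning alone.
- The protocol describes the trial in the past tense, so a change of wording may protect no child.
- The number affected may be zero, and there is no effect on inference.
- This is an inconsistency in drafting. No design decision is being challenged.

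**Conclusion.** The concern holds. As written, the two items cannot both be followed for a child withdrawn before six months because of an adverse event. This is a contradiction between two stated rules on patient care, so it is not a detail that a statistical analysis plan would supply.

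Its reach is narrow: one item against one item, for early adverse-event withdrawals only, among the 84 planned children. How many that is cannot be derived, because the protocol gives no adverse-event rate. Other early withdrawals fall under the termination item alone and are not affected.

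The conflict itself follows from the text and needs no numerical assumption. Only its practical timing rests on one, namely whether December 2020 to May 2021 is the enrolment period or the whole trial. Confidence is moderate, because an exception may have been intended and left unwritten.

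**What to change.** Reconcile item d of the Clinical Trial Process with items b and d of the adverse-event plan in one statement of what happens to the tuberculosis drugs when a child is withdrawn for an adverse event. That statement should say whether item d of the adverse-event plan depends on the liver condition in item b. The information for parents should then carry the same wording. Which clinical rule applies is for the investigators to decide, and this review takes no position on it.

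If treatment has already ended, the trial report should state which item was followed for children withdrawn because of an adverse event.

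The cost is one sentence in the protocol with matching wording for parents, or one sentence in the report. No change to the design, sample size or analysis is needed.

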Subject selection was determined based on consecutive sampling, namely the order of patients who came to the clinic until the minimum sample size (84 subjects) met the inclusion criteria. The exclusion criteria are children with a history of liver or kidney abnormalities, immunocompromised, and already received vitamin D supplementation. After obtaining written consent, all subjects had their blood specimens drawn 3cc from the brachial vein to measure alanine transaminase (ALT), alkaline phosphatase (ALP), serum active 25-hydroxyvitamin D using the ELISA method. Vitamin D is categorized as deficiency if serum 25-hydroxyvitamin D is below 20ng/mL, insufficiency between 20–30ng/mL, and normal levels above 30ng/mL. In this study, the 95% confidence level (Z α = 1.65 one-sided test) and 80% power test (Z β = 0.84) were selected. The calculation of the sample size above obtained n = 35 people for each group. The total study subjects were added by 20% of the minimum number of samples to compensate for loss-to-follow-up, so the total sample was 84, consisting of 42 patients in the intervention group and 42 patients in the placebo group.

For each subject, the following data were entered into the study database demographic data (name, age, sex), signs and symptoms (fever, cough), Tuberculin Skin Test (TST), Chest X-Ray, and also GeneXpert for Mycobacterium tuberculosis from gastric lavage or sputum induction, liver function test and 25-hydroxyvitamin D level. All results were recorded in a study database following international standards to protect the privacy and personal information.

Subjects were randomly assigned to receive either a 1000IU vitamin D supplement dose or a placebo with an allocation ratio of one to one. Before starting recruitment, the project manager prepared 84 packs of study preparation - 42 packs of the active study drug and 42 packs of a placebo, then generated a randomization sequence using a computer program assigning the terms active or placebo to numbers 1 to 84. The packs were then assigned a randomized number according to this computer-generated randomization sequence.

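### The adverse event recording item is scoped to side effects of the background antituberculosis drugs, so harms of the randomised product may go unreported

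*Protocol*

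**What the plan says.** In the Adverse Event (AE) reporting plan, item a gives as the things to be reported: "symptoms of side effects of antituberculosis treatment such as jaundice, nausea, and vomiting". It is the only item on what is to be recorded. The items that follow keep to the same subject. Item b calls for a liver function examination and states: "If the liver function increases, antituberculosis drugs will be discontinued". Item c tells families where to go with the same three symptoms. Item d, on leaving the study because of an adverse event, says that "the administration of antituberculosis drugs will be discontinued, and patients will not be included in the study".

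The Summary of Clinical Trial Protocol sets out the treatments. On the randomised contrast: "Subjects were randomly assigned to receive either a 1000IU vitamin D supplement dose or a placebo". On the background therapy: "All subjects received antimicrobial treatment for tuberculosis drugs in the form of a fixed-dose combination". The study product is taken daily for six months (Clinical Trial Process, item a).

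The Summary also describes a second route by which symptoms might be noted: "Monitoring of subjects medication adherence and daily symptoms conducted by using a checklist table". Parents complete it and the researcher confirms it at follow-up visits.

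**The concern.** In a placebo-controlled trial, the safety question that randomisation can answer is whether events differ between the study product and placebo. The recording item is built around a different treatment, one common to both arms. An event thought to come from the vitamin D, or from no drug at all, does not fit its description.

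Two things are at stake. First, a harm of the supplement might never enter the adverse event record. Second, the absence of a record could not be taken to mean the absence of an event, so a by-arm table built from these records would be hard to interpret. Children taking a daily supplement for six months are a group in whom a complete event record has obvious value, even where the trial's stated outcome is a laboratory level.

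**Working it through.** No arithmetic applies: the point concerns the scope of a recording rule and depends on no sample size, error rate or effect size. The check is to set the provisions side by side and ask whether any of them requires a harm of the randomised product to be recorded.

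1. **Item a of the AE plan.** The named symptoms are examples, so the list is open, but it is open within side effects of antituberculosis treatment. Vitamin D, placebo and study product are not mentioned.

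2. **Items b, c and d of the AE plan.** The work-up is of liver function, and the action and the discontinuation rule refer to antituberculosis drugs. Item c responds to complaints without asking their cause, but only for nausea, vomiting and jaundice, and it says where to attend, not what to record.

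3. **The parent checklist (Summary).** It is completed in both arms and carries no condition on cause. However, its symptom items are not given, and nothing says that an entry becomes an adverse event report.

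4. **The database list (Summary).** The signs and symptoms named are fever and cough, both features of the disease. No adverse event field is listed.

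5. **Six-month tests (Summary).** Vitamin D level and liver function are repeated in both arms. These are laboratory values at one time point and do not record clinical events. Under item d, a child withdrawn for an adverse event is no longer in the study and may not reach that test.

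6. **Unexpected events (Clinical Trial Process, item d).** They appear as a reason for not completing treatment and leaving the study. No instruction to record them follows.

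Provisions 2, 3 and 5 could capture some harms incidentally. None of the six requires an event possibly due to the study product to be recorded, and none asks for events regardless of cause.

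**The case against.** The best case for the plan is that item a is one terse line with examples, not a restrictive rule. The word *only* does not appear in it, and it could be read as naming target symptoms. Symptoms are also gathered in both arms without regard to cause through the parent checklist, confirmed at reviews on days 14, 28, 42 and 56 and monthly after that, and liver function is tested in all at six months. The only outcome indicator named is the vitamin D level, so no safety comparison is promised, and how events are tabulated may sit in an analysis plan that is not shown.

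Much of this stands as a limit on how far the point goes. A reader might infer three stronger things, and the document supports none of them:

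- *That harms of vitamin D are certain to be missed.* Nausea or vomiting caused by the supplement could be reported as an antituberculosis side effect, and the checklist may hold other symptoms.
- *That the protocol installs a causality judgement as a gate to recording.* The wording of item a is by attribution, but no assessor, criteria or assessment step is described.
- *That no safety comparison is possible.* Checklist entries and liver tests exist in both arms under concealed allocation.

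What does not stand is the suggestion that these routes repair item a. The checklist's contents and its link to reporting are both unstated. The analysis plan is no answer either: which events are collected is a protocol matter, and an analysis plan cannot tabulate what was not recorded.

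**Conclusion.** The point holds as one of scope. The protocol's single recording item describes side effects of the treatment that both arms share and leaves out the product under test, and no other provision requires harms of that product to be reported. They may therefore go unreported, and the adverse event records alone would not support a reliable comparison of vitamin D with placebo.

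The size of the loss cannot be estimated, because the document gives no expected event rate and does not say what the checklist contains. The stated outcome, the vitamin D level at six months, does not depend on this item.

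The conclusion rests on two readings: that item a, as the only recording item, sets the scope of reporting; and that the checklist does not feed adverse event reports, since nothing says it does. If the checklist asks about general symptoms and was in practice used for event reporting, the gap is smaller and the protocol should say so.

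**What to change.** Reword item a so that every adverse event in either arm is recorded whatever its suspected cause, drawing on the parent checklist and clinic reviews already planned. State that checklist entries feed the adverse event record, and add an adverse event field to the database. For each event, have the blinded clinician note suspected relation to the antituberculosis drugs and to the study product separately. Tabulate events by randomised arm.

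The cost is a rewritten item, a few more lines on an existing form and slightly more data entry. No new test or clinical management rule is needed.

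Timing matters. The Summary dates the study from December 2020 to May 2021, and the document was last updated on 1 June 2021. If data collection is complete, rewording cannot recover events that were never noted. In that case, extract symptoms by arm from the completed checklists and clinic records, and state in the report that adverse event recording was scoped to antituberculosis side effects.
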